### 4.2.8.3 Nights with awakening due to asthma

The change from baseline in the bi-weekly mean number (percentage) of nights with awakening due to asthma that required rescue medication will be summarized as described in Section 4.2.5.1 for the descriptive statistics only – there won't be any MMRM.

#### 4.2.8.4 Rescue medication use

The change from baseline in bi-weekly mean rescue medication use will be summarized as described in Section 4.2.5.1 for the descriptive statistics only – there won't be any MMRM.

The number and percentage of subjects within each treatment group who received rescue medication will be summarized by each bi-weekly period.

#### 4.2.8.5 Home PEF (morning and evening)

The percent change from baseline in bi-weekly mean morning and evening PEF will each be summarized as described in Section 4.2.5.1 for the descriptive statistics only – there won't be any MMRM.

#### 4.2.8.6 SNOT-20

The change from baseline in SNOT-20 will each be summarized as described in Section 4.2.5.1. Percentage of subjects answering "most important" in SNOT-20 questionnaire will summarized by treatment group and planned visit.

# 4.2.9 Safety and tolerability

All safety variables will be summarized using the safety analysis set and data presented according to treatment randomized.

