## 8.3.2 Safety analysis set

Safety analysis set (Safety): All subjects who received any investigational product will be included in the safety analysis set. Subjects will be classified according to the treatment they actually received. A subject who has on one or several occasions received active treatment will be classified as active. All safety summaries will be based on this analysis set.

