# 1. STUDY DETAILS

This is the statistical analysis plan (SAP) for study D2210C00014. The SAP describes the statistical analyses specified in the clinical study protocol (CSP) in more detail; any changes with regards to what is already specified in the CSP will be described in Section 6.

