#### 2.1.2 Safety analysis set

Safety analysis set (Safety): All subjects who received any IP will be included in the safety analysis set. Subjects will be classified according to the treatment they actually received. A subject who has, on one or several occasions, received active treatment will be classified as active. A subject who has received only Placebo will be classified as Placebo. All safety and ADA summaries will be based on this analysis set.

Any deviation from the randomized treatment assignment will be listed and considered when interpreting the safety data.

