#### 2.2 Violations and deviations

Only important protocol deviations will be listed and tabulated in the CSR for all randomized subjects. These are protocol deviations that may greatly impact the completeness, accuracy, and/or reliability of the study data or that may significantly affect a subject's rights, safety, or well-being include:

- Subjects who do not meet the inclusion criteria
- Subjects who do not meet the randomization criteria
- Subjects who meet any of the exclusion criteria
- Subjects who use one or more disallowed medication, or restricted medications outside of the restrictions defined in the CSP, (for any reason, unless otherwise specified) during the randomized treatment period
- Subjects who received the incorrect IP or study dose at any time during the 12-Week double-blind treatment period
- Subjects who developed withdrawal criteria during the study but were not withdrawn from IP

All important protocol deviations will be identified and documented by the AZ study physician and statisticians prior to unblinding of the data.

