#### 4. ANALYSIS METHODS

#### 4.1 General principles

The analysis of the study endpoints will include all data captured during the 12-week doubleblind treatment period. This includes data regardless of whether IP was prematurely discontinued or delayed, and/or irrespective of protocol adherence, unless the subject withdraws consent to study participation.
Only exacerbations confirmed to meet the protocol definition (CSP Section 5.1.12) will be included in exploratory summaries. This includes only exacerbations that started on or after the date of randomisation, and those that are defined as a worsening of asthma that leads in at least one of the three criteria detailed in protocol Section 5.1.12 being fulfilled. This will include exacerbations where the eCRF exacerbation records a new/worsened symptom, requiring systemic corticosteroid intervention or hospitalization.

A summary table which counts subjects who have been incorrectly randomized and who received incorrect treatment will be presented.

Summary data will be presented in tabular format by treatment. Categorical data will be summarized by the number and percentage of subjects in each category. Continuous variables for parametric data will be summarized by descriptive statistics including N, mean, standard deviation (SD), geometric mean, SD of log values, median, minimum and maximum. All data will be listed. Data listings will be sorted by treatment and subject number.

Measures of location (mean, geometric mean, median, minimum and maximum) will be reported to the same degree of precision as the raw data unless otherwise stated. Measures of spread (SD) will be reported to one further degree of precision.

Continuous descriptive statistics for the percent and absolute change from baseline will summarize N, mean, SD, median, minimum and maximum and will be based on raw data. Continuous descriptive statistics for the ratio will summarize N, geometric mean and SD of log values and will be based on log-transformed data. Primary and secondary efficacy variables will summarise the ratio, absolute and percent change, exploratory efficacy variables will summarise absolute and percent change, and non-efficacy summary statistics on the change from baseline will only present the absolute change.

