### 4.2.3 Exposure and Compliance

Extent of exposure to IP is defined as the number of days between the start and the end dates of study therapy plus 14 days:

Extent of exposure (days) = (Last dosing date + 14 days) - First dosing date + 1.

In addition, the total number of dosing occasions is calculated by summing the doses taken by the subject. The total number of dosing occasions expected is defined as:

*Total number of dosing occasions expected = number of visits during treatment phase the subject attended.* 

Compliance is defined as:

Compliance (%) = (Total number of dosing occasions/total number of dosing occasions expected) x 100

Extent of exposure to IP, compliance and total number of dosing occasions will be summarized by treatment group, using the safety analysis set.

Compliance with the regularly scheduled ICS/LABA asthma inhaler as recorded in the daily diary will be summarized by each bi-weekly period and treatment group, together with the compliance of the use of the daily diary.

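### SAP 4.2.9 presents safety data by randomized arm, while SAP 2.1.2 and protocol 8.3.2 classify the same analysis set by treatment received

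*SAP*

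**What the plan says.** SAP Section 4.2.9, which opens the safety and tolerability analyses, reads: "All safety variables will be summarized using the safety analysis set and data presented according to treatment randomized".

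SAP Section 2.1.2 defines that same set differently: "Subjects will be classified according to the treatment they actually received". It adds that one or more active doses make a subject active and that only-placebo subjects count as placebo, and it places all safety and ADA summaries on this set. It also provides that "Any deviation from the randomized treatment assignment will be listed and considered when interpreting the safety data".

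Protocol Section 8.3.2 has the same as-received rule, including the mixed-exposure clause: "A subject who has on one or several occasions received active treatment will be classified as active".

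SAP Section 1 commits that "any changes with regards to what is already specified in the CSP will be described in Section 6". Section 6 goes down to details such as the number of decimals for p-values and the urinalysis categories, but has no entry on how safety data are grouped.

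**The concern.** One set of tables cannot follow both rules. They part for two kinds of subject: someone randomized to placebo who received any tralokinumab, and someone randomized to tralokinumab who received only placebo. A tralokinumab-randomized subject who received some placebo doses by mistake is active under both.

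The SAP treats the triggering event as possible. Section 2.2 lists among the important deviations "Subjects who received the incorrect IP or study dose at any time during the 12-Week double-blind treatment period", and the mixed-exposure clause in 2.1.2 would serve no purpose if safety tables were always by randomized arm.

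At stake is attribution. Adverse events, injection-site reactions, hypersensitivity events and ADA results in a subject exposed to tralokinumab would be shown under placebo. If the choice is left open, the arm of such a subject could be settled with unblinded data in view.

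Other outputs may also fail to match. SAP Section 4.2.3 says "Extent of exposure to IP, compliance and total number of dosing occasions will be summarized by treatment group, using the safety analysis set" and does not repeat the randomized-treatment wording, so exposure tables could follow 2.1.2 while the adverse event tables follow 4.2.9. The PK set in SAP Section 2.1.3 is defined by receipt of tralokinumab, so the same subject could contribute drug concentrations while sitting in the placebo safety column.

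**Working it through.** The plan gives no figure of its own on this point. The check is a comparison of the rules, followed by an illustration of scale.

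**Step 1. Assignment under each rule**

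| Randomized to | Received | SAP 2.1.2 / protocol 8.3.2 | SAP 4.2.9 |
|---|---|---|---|
| Tralokinumab | Tralokinumab only | Active | Active |
| Tralokinumab | Some of each | Active | Active |
| Tralokinumab | Placebo only | Placebo | Active |
| Placebo | Any tralokinumab | Active | Placebo |
| Placebo | Placebo only | Placebo | Placebo |

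Rows three and four conflict.

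**Step 2. Effect of one misdosed subject**

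Input: 40 subjects planned per arm (protocol Section 3.3). Assume one placebo-randomized subject receives tralokinumab and is the only subject with a given reaction. Differences are active minus placebo.

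- SAP 4.2.9: 0/40 - 1/40 = -2.50 percentage points.
- SAP 2.1.2: 1/41 - 0/39 = +2.44 percentage points.
- Swing: 2.44 + 2.50 = 4.94 percentage points, with a change of sign.

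Mirror case, a tralokinumab-randomized subject given only placebo who has the sole event:

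- SAP 4.2.9: 1/40 - 0/40 = +2.50 points.
- SAP 2.1.2: 0/39 - 1/41 = -2.44 points.

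With 1, 2 or 3 placebo-randomized subjects reclassified, the as-received denominators are 41/39, 42/38 or 43/37, against 40/40 as randomized.

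**Step 3. How likely is it that the rules diverge?**

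The documents give no dosing-error rate, so the rate p per dosing occasion is an assumption. Six doses (weeks 0, 2, 4, 6, 8 and 10) for 40 placebo subjects give 40 × 6 = 240 occasions. Assuming full dosing and independent errors, the chance that at least one placebo subject receives any active dose is 1 - (1 - p)^240.

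| Assumed p | Chance of at least one reclassified placebo subject |
|---|---|
| 0.01% | 2.4% |
| 0.05% | 11.3% |
| 0.1% | 21.3% |
| 0.5% | 70.0% |

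Under the same model, a tralokinumab-randomized subject who completes dosing on placebo alone needs six consecutive errors. At p = 0.5% that is 0.005^6, about 1.6 × 10^-14 per subject.

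**The case against.** The strongest reply is that the SAP already implies which rule wins. It says it details the protocol's analyses and records departures in Section 6. The protocol specifies as-received grouping, 2.1.2 repeats it, and Section 6 records no departure, so a careful programmer would follow 2.1.2. This supports reading 4.2.9 as a slip and points to the right correction. It is an inference, however: no clause states precedence, and 4.2.9 is an explicit instruction in the very section from which the safety tables will be programmed.

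Second, safeguards exist. Besides the listing in 2.1.2 and the deviation reporting in 2.2, SAP Section 4.1 promises that "A summary table which counts subjects who have been incorrectly randomized and who received incorrect treatment will be presented". In a study of about 80 subjects, a misdosed subject would be easy to spot. That is true, but visibility in a listing does not move the subject to the correct column.

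Third, the practical weight is modest. Safety is descriptive, so no test or decision rule depends on it. An unblinded IP manager and administrator handle visually distinct products (protocol Section 3.6). The assumed error rates span almost any conclusion, and the 70% figure only reflects the top of the range. The mirror case is realistic only after very early discontinuation or a systematic allocation error. All of this stands and limits the size of the point.

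Fourth, the term treatment group in 4.2.3 also appears in the subsections of 4.2.9, so it does not show that two treatment variables are intended. The exposure mismatch is therefore a possibility under a literal reading, not an established feature of the plan.

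**Conclusion.** The concern holds. SAP 4.2.9 states a grouping rule that contradicts the definition of the set it uses, in both the SAP and the protocol, and the departure is not declared. Confidence in the textual conflict is high.

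The consequence is conditional. It is nil if nobody receives the wrong product, and it is a 4.9-point swing with a reversed sign for a single event in a single misdosed placebo subject, given 40 per arm. How often that would arise cannot be read from the documents; the probabilities above rest on assumed error rates and independence between doses. The point concerns safety and ADA summaries only. The full analysis set efficacy analyses, including blood eosinophils, are correctly by randomized arm. This should be corrected, but it does not threaten the trial's main conclusion.

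**What to change.** In SAP Section 4.2.9, replace the reference to randomized treatment with treatment actually received as defined in Section 2.1.2. State that this applies to every output under 4.2.9, including immunogenicity in 4.2.9.7. Keep the full analysis set efficacy analyses as randomized. If presentation by randomized arm was in fact intended, the alternative is to amend 2.1.2 and record the departure from protocol Section 8.3.2 in SAP Section 6.

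The cost is one sentence in the SAP and the choice of treatment variable in the safety programs. It should be settled before unblinding.

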## 4.2.9.1 Adverse events (AEs)

AEs will be summarized separately for the treatment and study periods. AEs occurring during the run-in period, or occurring post-treatment (as per the definition in Section 3.4.1) will be listed, but not summarized separately.

An overall summary table will be produced showing the number and percentage of subjects with at least 1 AE in any of the following categories; AEs, SAEs, deaths due to AE, AEs causing discontinuation of IP (DAEs), and other significant AEs (OAEs). OAEs will be defined following medical review of system organ classes/preferred terms after unblinding of the data. The total number of AEs in the different AE categories in terms of AE counts will also be presented (ie, accounting for multiple occurrences of the same event in a subject).

AEs will be summarized by SOC and PT assigned to the event using MedDRAversion 20.0. For each PT, the number and percentage of subjects reporting at least one occurrence will be presented ie, for a subject multiple occurrences of an AE will only be counted once.

AEs (by SOC and PT) will be summarized by causality and maximum intensity. If a subject reports multiple occurrences of the same AE, the maximum intensity will be taken as the

highest recorded maximum intensity (the order being mild, moderate, and severe). AEs with missing intensity will not be outputted in this table.

The following will also be summarized by SOC and PT

SAEs OAEs in the category of safety topics of special attention DAEs DAEs causally related to IP SAEs leading to discontinuation of IP Most common AE's (frequency of >3%) (by PT only) Deaths Severe Infections Severe infections will be identified as AEs that have been entered into the infection modules in the eCRF (INFDI, INFRF and INFSS).

Injection site reactions will be reported by preferred term for the treatment period, summarized by treatment group.

The approach to identifying anaphylaxis/hypersensitivity AEs occurring within 3 days of IP administration is described in a separate charter. Those identified AEs meeting the criteria described in this charter will be summarized by preferred term and treatment group for the treatment period and study period.

Subjects experiencing a severe infection are defined as having an AE which met one of the following:

- life-threatening,
- requiring hospitalisation,
- requiring treatment with antiviral medications, intravenous antibiotics or medications for helminth parasitic infections,
- permanent discontinuation of study drug.

Severe infections will be summarized by MedDRA high level group term, high level term and preferred term by treatment group for the treatment period and study period.

The rate of AEs per person-years at risk, calculated as (number of subjects reporting AE)/(total time at risk of AE), will also be reported. Rates will typically be expressed in terms of events per 100 subject-years. Total time at risk will be defined as the date of last visit in the 12-week treatment period – date of randomization +1.

Separate listings of subjects with AEs, SAEs, death due to AE, discontinuations due to AEs, or severe infections will be presented.

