# 3.6 Methods for ensuring blinding

This is a double-blind study in which tralokinumab and placebo are visually distinct from each other. Neither the subject nor any of the Investigator or sponsor staff who are involved in the treatment or clinical evaluation and monitoring of the subjects will be aware of the treatment

received. Since tralokinumab and placebo are visually distinct, IP will be handled by an unblinded IP manager at the site and will be administered by an unblinded investigational site study team member who will not be involved in the management of study subjects (this could be the same person).

Should an issue arise with the IP (e.g. damaged kit or syringe) that has been assigned to a subject prior to administration, or any other unexpected event with the kit or syringe (e.g. a malfunction during IP administration) the unblinded IP manager at the site will contact a predetermined unblinded AstraZeneca site monitor (who is not otherwise involved in the project) to determine whether any specific actions are required.

A blinded AstraZeneca site monitor will perform IP accountability. In the event that the treatment allocation for a subject becomes known to the Investigator or other study staff involved in the management of study subjects, or needs to be known to treat an individual subject for an AE, the sponsor must be notified immediately by the Investigator and if possible, before unblinding.

All packaging and labelling of IP will be done in such way as to ensure blinding for all sponsor and investigational site staff (other than the unblinded IP manager who will directly handle the pre-filled syringes).

The following personnel will have access to the randomization list:

- IVRS/IWRS Vendor
- those generating the randomization list

The information in the randomization list will be kept from other personnel involved in the conduct of the study, and in a secure location until the end of the study.

No member of the extended study team at AstraZeneca, or any contract research organization (CRO) handling data, will have access to unblinded information during the conduct of the study, with the exception of the Supply Chain Study Management department and the Patient Safety department at AstraZeneca.

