## 8.4.5.2 Other significant adverse events

During the evaluation of the AE data, an AstraZeneca medically qualified expert will review the list of AEs that were not reported as SAEs or discontinuations due to AEs.

Based on the expert's judgment, significant AEs of particular clinical importance may, after consultation with the Global Patient Safety Physician, be considered other significant AEs (OAEs) and reported as such in the CSR.

Examples of these are marked haematological and other laboratory abnormalities, and certain events that led to intervention (other than those already classified as serious), dose reduction, or significant additional treatment.

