#### **3.4.2** Safety topics of special attention

Although the CSP did not describe AEs of special interest, AstraZeneca Patient Safety and study physicians will review all AEs and identify those that merit special attention. These AEs fall into three categories, AEs possibly related to administration of biologics (e.g., anaphylaxis/hypersensitivity reactions and injection site reactions), AEs possibly related to the mechanism of action of tralokinumab as an IL-13 blocking agent (e.g., infections such as

severe, viral, invasive fungal, and parasitic, malignancy, cardiovascular/cerebrovascular events, pregnancy/spontaneous abortion and increased eosinophils) and AEs reported for other biologics in this class (e.g., musculoskeletal). AEs falling into the category of safety topics of special attention will be tabulated.

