# 6. CHANGES OF ANALYSIS FROM PROTOCOL

A number of clarifications and minor corrections have been made and are listed below:

- Section 3.4.3/4.2.9.2: due to the way the data is collected on the eCRF, the urinalysis categories have been updated to negative, trace or positive.
- The presentation of asthma exacerbations is not detailed in the protocol. This has been added as an exploratory variable (Section 1.1.4) and some text detailing summaries that will be provided have been included In addition, a start and end date definition of an exacerbation has also been added.
- Section 3.3.1.5: Categorisation of Improved/ No Change/ Deterioration has be relabelled as ACQ-6 Response to be distinct from ACQ-6 Responder which is Yes or No.
- Section 1.1.4 p.15: The analysis is now calculate the change from baseline up to Week 12 in fractional exhaled nitric oxide ( $FE_{NO}$ )
- Section 3.1.1: Baseline for Asthma Daily Diary variables will be, for each variable, the average of all the daily records within the 14 days prior to randomization
- Section 3.2.3.1 to Section 3.2.3.3: ratios will also be calculated for sputum, serum, large and small airways remodelling variables
- Section 3.3.1.3: Bi-weekly mean number of nights is expressed as a percentage
- Section 3.4.1 and 4.2.2: increased follow-up period to 20 weeks
- Section 1.1.4 and 3.2.3.2, 3.2.3.3: The three types of change from baseline analyses (absolute, percent, ratio) will be performed for all exploratory endpoints.
- Section 3.2.3.1: Removed analysis of soluble biomarkers, serum biomarker, nasosorption biomarkers, airway epithelial gene expression, airway volume and resistance based on FRI, effect of Tralo on RNA.
- Removed references to sub-sub segmental as team will be combining sub-segmental and sub-sub-segmental analyses together.
- SNOT-20 is coming from RAVE, and not from the e-diary data.
- The change in sputum eosinophils as percentage number of inflammatory cells won't be analysed (this was a supportive secondary outcome measure added in protocol amendment 2).
- MMRM only performed on secondary efficacy; not on efficacy

- Section 2.1.3: The definition of PK analysis set has been updated to include subjects in FAS who received tralokinumab and had blood samples obtained for PK.
- Section 3.4.2: The OAEs have been updated to safety topics of special attention
- Section 4.1: Under general principles, the p-values rounding has been updated from 3 to 4 decimal places (reference CSP section: 8.5).

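### The SAP defines other significant AEs by medical review after unblinding and does not keep the reviewers blinded, so knowledge of the arms could influence which events are labelled

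*SAP*

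**What the plan says.** Protocol 8.4.5.2 introduces other significant AEs (OAEs). For this, "an AstraZeneca medically qualified expert will review the list of AEs that were not reported as SAEs or discontinuations due to AEs". Selection is by that expert's judgement of clinical importance, after consulting the Global Patient Safety Physician. Examples are given, but no closed list.

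SAP 3.4.2 brings in safety topics of special attention: "AstraZeneca Patient Safety and study physicians will review all AEs and identify those that merit special attention". Three categories follow (administration of biologics, the IL-13 mechanism, and events reported for other biologics in the class), each illustrated by examples only. SAP 6 declares the link: "Section 3.4.2: The OAEs have been updated to safety topics of special attention".

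SAP 4.2.9.1 nevertheless keeps OAEs as a separate category in the overall summary table, beside AEs, SAEs, deaths and AEs causing discontinuation of IP. It sets the timing: "OAEs will be defined following medical review of system organ classes/preferred terms after unblinding of the data". The same section also tabulates, by system organ class and preferred term, OAEs falling under the special-attention topics.

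**The concern.** OAE status is a matter of judgement, and the SAP places that judgement after the codes are broken. A reviewer who can see how events fall by arm may, without intending to, find a term more or less noteworthy because of that split. The by-arm OAE count would then partly reflect the reviewers' knowledge of the result. The influence could run in either direction.

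The timing also departs from the SAP's own practice for comparable judgements. What is at stake is the neutrality of one highlighted category and of the special-attention tables. The completeness of the safety data is not in question.

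**Working it through.** The plan attaches no figure to this step, so the main check is to compare the passages.

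**1. When are judgement-based classifications made?**

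| Classification | Section | Timing or rule |
|---|---|---|
| Important protocol deviations | SAP 2.2 | "All important protocol deviations will be identified and documented by the AZ study physician and statisticians prior to unblinding of the data" |
| Disallowed medications | SAP 4.2.2 | Programming plus physician review before database lock |
| Anaphylaxis/hypersensitivity | SAP 4.2.9.1 | Criteria in a separate charter |
| Severe infections | SAP 4.2.9.1 | Infection eCRF modules and stated criteria |
| Safety topics of special attention | SAP 3.4.2 | Sponsor review; timing not stated |
| OAEs | SAP 4.2.9.1 | Medical review after unblinding |

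Of these, OAE selection is the only one expressly placed after unblinding.

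**2. Are the reviewers blinded?** No section says so for this review. SAP 3.4.2 names Patient Safety among the reviewers. Protocol 3.6 bars the study team from unblinded information during the study, "with the exception of the Supply Chain Study Management department and the Patient Safety department at AstraZeneca". An earlier date alone would therefore not guarantee a blinded review.

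**3. Do the sections agree on what an OAE is?** Not fully. Protocol 8.4.5.2 draws OAEs from events that are neither SAEs nor discontinuations due to AEs. SAP 3.4.2 reviews all AEs. SAP 6 says the one concept has become the other. SAP 4.2.9.1 uses both, and its timing sentence mentions OAEs only. SAP 6 does not list the post-unblinding timing among the changes.

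**4. What does the OAE choice leave unchanged?** SAP 4.2.9.1 summarises AEs by system organ class and preferred term, and by causality and maximum intensity. SAEs, deaths, discontinuations and AEs above 3% frequency are summarised as well, and listings are produced. The protocol synopsis makes all safety analyses descriptive.

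**5. Illustration only: chance differences in single terms.** Inputs: 40 subjects per arm (SAP 1.3). The number of terms K and a common true incidence p, equal in both arms, are assumptions found in neither document. Terms are taken as independent. With X and Y each Binomial(40, p) and F the distribution function of X − Y, the expected largest excess on tralokinumab over K terms is Σ d·[F(d)^K − F(d−1)^K] subjects, divided by 40.

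For K = 20:
- p = 3%: 2.86 subjects; 2.86/40 = 7.1 percentage points
- p = 5%: 3.64 subjects; 3.64/40 = 9.1 points
- p = 10%: 5.00 subjects; 5.00/40 = 12.5 points

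For K = 10 the three values are 5.8, 7.4 and 10.3 points; for K = 40 they are 8.4, 10.6 and 14.5. By symmetry the largest deficit has the same size. The calculation shows only that differences of this order between arms would be visible in some preferred term even if the drug had no effect on any of them.

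**The case against.** The strongest defence is that little depends on the label. Every event appears in the full tables and listings whether or not it is called an OAE, and safety is not tested. Severe infections and anaphylaxis/hypersensitivity are governed by their own rules, and injection site reactions have their own table. This stands, and it limits the point to labelling and emphasis.

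Second, the choice is not unbounded. SAP 3.4.2 and SAP 6 tie it to three named categories. This stands in part: the examples are open-ended, so discretion remains inside the categories.

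Third, a reader might infer that the reviewers will hold the allocation codes. The text does not say this. It says only that the review follows unblinding of the data and covers system organ classes and preferred terms. What the documents support is narrower: nothing prevents the reviewers from knowing the arms.

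Fourth, a reader might infer that the SAP contradicts the protocol on timing. It does not. The protocol says only "During the evaluation of the AE data, an AstraZeneca medically qualified expert will review the list of AEs", with no reference to unblinding.

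Fifth, some safety signals can be recognised only by arm. That is a fair reason to permit later additions, but not to leave the whole category undefined until then.

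**Conclusion.** The point holds as a minor to moderate reporting issue, worth correcting. The SAP sets a judgement-based AE category after unblinding, does not blind the people who set it, and reports the result by arm. It rests on one modest assumption: that reviewers working after unblinding, with no provision to keep them blinded, may know the arms.

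Two stronger readings go beyond the documents. One is that an imbalance could be hidden. It could not be removed from the report, because each preferred term is tabulated in any case; only its prominence could change. The other is that the differences in step 5 measure the bias. They concern the largest difference in a single term under assumed incidences. The OAE row counts subjects with at least one event pooled over the selected terms, and the protocol's criterion is clinical importance rather than difference between arms. No bias in that row can be computed from the documents. The primary and secondary efficacy results and the type I error are unaffected.

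**What to change.** Replace the timing sentence in SAP 4.2.9.1 with a rule that OAE and special-attention terms are identified by reviewers who have no access to treatment allocation, and that the term list is documented and signed off before database lock and unblinding. Because of the Patient Safety exception in protocol 3.6, state the reviewers' blinding explicitly and do not rely on the date alone. Allow terms to be added after unblinding, labelled post hoc.

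Align protocol 8.4.5.2 with SAP 3.4.2, 4.2.9.1 and 6 on whether OAEs and special-attention topics are the same thing, whether SAEs and discontinuations are in the pool, and when the decision is made.

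The cost is small: a review already planned is brought forward, and preparing and signing off the term list becomes an extra deliverable before lock. No new data are needed.
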